### **7.6.6 Adverse Events**

Adverse events will be summarized by treatment group.

The following analyses will be conducted using the 30 days safety window only:

- Overall summary of any AEs by worst CTC grade (1, 2, 3, 4, 5, not reported, total) presented by SOC/PT.
- Overall summary of any AEs presented by worst CTC grade (any grade, grade 3-4, grade 5) by SOC/PT. This table will be restricted to events with an incidence greater or equal to 5% in any treatment group.
- Overall summary of any non-serious AEs presented by SOC/PT. This table will be restricted to events with an incidence greater or equal to 5% in any treatment group.
- Overall summary of any AEs that required immune modulating medication by worst CTC grade (any grade, grade 3-4, grade 5) presented by SOC/PT.
- Overall summary of drug-related AEs by worst CTC grade (1, 2, 3, 4, 5, not reported, total) presented by SOC/PT.

The following analyses will be conducted using the 30 days safety window and repeated using the 100 days safety window:

- Overall summary of drug-related AEs by worst CTC grade (any grade, grade 3-4, grade 5) presented by SOC/PT.

A by-subject AE listing will be provided. A by-subject listing of any AE requiring immune modulating medications will also be provided.

### **7.6.7 Select Adverse Events (EU/ROW Submissions)**

Unless otherwise specified, analyses will be performed by select AE category. Analyses will also be repeated by subcategory of endocrine events.

#### **7.6.7.1 Incidence of Select AE**

Select AEs will be summarized by treatment group for each category/subcategory.

The following analyses will be conducted using the 30-day safety window only:

- Overall summaries of any select AEs by worst CTC grade (any grade, grade 3-4, grade 5) presented by Category or Subcategory/PT.
- Overall summaries of any drug-related select AEs by worst CTC grade (any grade, grade 3-4, grade 5) presented by Category or Subcategory/PT.
- Overall summaries of any serious select AEs by worst CTC grade (any grade, grade 3-4, grade 5) presented by Category or Subcategory /PT.
- Overall summaries of drug-related serious select AEs by worst CTC grade (any grade, grade 3-4, grade 5) presented by Category or Subcategory /PT.
- Overall summaries of any select AEs leading to discontinuation by worst CTC grade (any grade, grade 3-4, grade 5) presented by Category or Subcategory /PT.
- Overall summaries of drug-related select AEs leading to discontinuation by worst CTC grade (any grade, grade 3-4, grade 5) presented by Category or Subcategory /PT.
- Summary of frequency of unique select AEs by Category.

A by-subject select AE listing will be provided.

#### **7.6.7.2 Time-to Onset of Select AE**

Time-to onset of drug-related select AEs (any grade, grade 3-5) will be summarized for each category/subcategory by treatment group.

Time-to onset analyses are restricted to treated subjects who experienced at least one drug-related select AE in the category/subcategory. The analyses will be conducted using the 30-day safety window.

Additional details regarding the time-to onset definition are described in time-to onset definition subsection of [APPENDIX 1](#).

#### **7.6.7.3 Time-to Resolution of Select AE**

Time-to resolution of the following specific events will be summarized separately for each category/subcategory.

- Time-to resolution of drug-related select AE (any grade, grade 3-5) by treatment group.
- Time-to resolution of drug-related select AE (any grade, grade 3-5) where immune modulating medication was initiated, by treatment group.

Time-to resolution analyses are restricted to treated subjects who experienced the specific events. Time-to resolution where immune modulating medication was initiated analyses are restricted to treated subjects who experienced the specific events and who received immune modulating medication during the longest select AE.

The analyses will be conducted using the 30-day safety window.

The following summary statistics will be reported: percentage of subjects with resolution of the longest select AE, median time-to resolution along with 95% CI (derived from Kaplan-Meier estimation) and ranges.

See time-to resolution definition subsection of [APPENDIX 1](#) for additional details.

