### **Time-to resolution definition**

In order to derive the time-to resolution, overlapping or contiguous AEs within a specific category or subcategory will be collapsed into what will be termed “clustered” AEs. For example, if a subject (without pre-treatment AE) experienced an AE from 1st to 5th January, another AE (with different PT but within same category) from 6th to 11th January and same AE from 10th to 12th January, these will be collapsed into one clustered AE from 1st to 12th January. [Table 8-1](#) is summarizing key derivation steps for each type of clustered AEs.

Time-to resolution of AE (any grade) for a specific category is defined as the longest time from onset to complete resolution or improvement to the grade at baseline among all clustered AEs experienced by the subject in this category per adverse event criteria category. Events which worsened into grade 5 events (death) or have a resolution date equal to the date of death are considered unresolved. If a clustered AE is considered as unresolved, the resolution date will be censored to the last known alive date. Improvement to the grade at baseline implies that all different events in the clustered adverse event should at least have improved to the corresponding (i.e. with same preferred term) baseline grade. This measure is defined only for subjects who experienced at least one AE in the specific category.

The time-to resolution of AE (grade 3-5) for a specific category is defined similarly with an onset date corresponding to a grade 3-5 AE.

Time-to resolution of drug-related AE (any grade or grade 3-5) for a specific category is defined similarly but restricted to drug-related AE.

The time-to resolution of AE (any grade or grade 3-5, drug-related or all) where immune modulating medication was initiated is defined similarly. For data presentation not restricted to IMAE, the additional condition that the subject started an immune modulating medication during the longest AE resolution period will be applied.

Time-to resolution for a specific subcategory is defined similarly but restricted to event of this subcategory.

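### The select-AE resolution table for participants given immune-modulating medication leaves out those whose treated episode was shorter than a separate untreated one, and percent resolved can miss a shorter ongoing episode

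*SAP*

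**What the plan says.** SAP 7.6.7.3 plans two time-to-resolution summaries of drug-related select AEs, each for any grade and for Grade 3-5. One covers all participants with such an event. The other covers "treated subjects who experienced the specific events and who received immune modulating medication during the longest select AE". Both report the "percentage of subjects with resolution of the longest select AE, median time-to resolution along with 95% CI".

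Appendix 1 supplies the derivation:

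- Clustering comes first: "overlapping or contiguous AEs within a specific category or subcategory will be collapsed into what will be termed" clustered AEs.
- Time to resolution is then "the longest time from onset to complete resolution or improvement to the grade at baseline among all clustered AEs experienced by the subject" in that category.
- Ongoing events are kept: "If a clustered AE is considered as unresolved, the resolution date will be censored to the last known alive date".
- Fatal events are kept too: "Events which worsened into grade 5 events (death) or have a resolution date equal to the date of death are considered unresolved".
- For the IMM version, in presentations not restricted to immune-mediated AEs (IMAEs), "the additional condition that the subject started an immune modulating medication during the longest AE resolution period will be applied".

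Section 7.6.7.3 speaks of medication received and Appendix 1 of medication started; I read these as one condition. Table 8-1 excludes a cluster with no Grade 3-5 record from the Grade 3-5 derivations.

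**The concern.** The IMM table should describe how long select AEs last once IMM is given. As derived, the longest cluster is picked from all clusters, treated or not, and the participant is kept only if that cluster happens to be a treated one. A treated episode that clears faster than a separate untreated episode therefore takes its participant out of the table. Selection depends on the outcome, and the treated durations that remain lean long.

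The table can also cover fewer participants than SAP 7.4.3.1 reports as given IMM for drug-related select AEs in the same category, with no stated reason for the gap.

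Percent resolved has a related weakness. A participant with a resolved cluster and a second, still ongoing cluster that is shorter so far counts as resolved. For a toxicity summary this errs in the favourable direction.

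Repeat episodes are foreseeable. Protocol 7.4.4.2 allows nivolumab to resume after recovery, and SAP 7.6.8 plans re-challenge summaries.

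**Working it through.** The plan states no figure on this point. I traced the derivation on invented data, then asked how large the effect could be in the participants it touches.

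**1. Five invented participants, any grade, one category (days)**

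| Participant | Clusters | Longest cluster | In IMM table? |
|---|---|---|---|
| P1 | untreated 40 resolved; treated 14 resolved | 40, untreated | No |
| P2 | treated 30 resolved | 30, resolved | Yes |
| P3 | treated 60 ongoing | 60, censored | Yes |
| P4 | treated 30 resolved; treated 20 ongoing | 30, resolved | Yes |
| P5 | treated 21 resolved | 21, resolved | Yes |

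- SAP rule: n = 4, resolved 3/4 = 75.0%. Kaplan-Meier: 0.75 at day 21, then 0.75 × (1 − 2/3) = 0.25 at day 30, so the median is 30.
- Longest treated cluster per participant: n = 5, resolved 4/5 = 80.0%, median 30.
- All treated clusters resolved: 3/5 = 60.0%.

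P1 is lost although treated. P3, ongoing and longest, stays in as censored and unresolved. P4 counts as resolved although one episode is ongoing. The median happens not to move here. If P1's 40-day cluster had no Grade 3-5 record and the 14-day one did, P1 would be kept in the Grade 3-5 table.

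**2. Conditional size, IMM table.** Assumptions, not from the documents: two separate clusters in a category, exactly one treated, independent exponential durations, treated mean 30 days, untreated mean m, no censoring. The share kept is P(treated > untreated) = 30/(30 + m). The median of all treated clusters is 30 × ln 2 = 20.8 days.

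| m (days) | Kept | Dropped | Median of those kept (simulated) |
|---|---|---|---|
| 15 | 30/45 = 67% | 33% | 31.7 |
| 30 | 30/60 = 50% | 50% | 36.9 |
| 60 | 30/90 = 33% | 67% | 41.6 |

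Check for m = 30: those kept have distribution function (1 − e^(−t/30))², so the median is −30 × ln(1 − √0.5) = 36.8.

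**3. Conditional size, percent resolved.** Same exponential model, both means 30 days, first cluster resolved, second censored uniformly between a and b days:

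- P(second ongoing) = 30/(b − a) × (e^(−a/30) − e^(−b/30))
- P(second ongoing and hidden behind a longer first) = 15/(b − a) × (e^(−a/15) − e^(−b/15))

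Follow-up for a fully dosed nivolumab participant, scheduled visits only: the last infusion is on day 4 × 28 + 1 = 113, the last oral study dose about day 140, the 30-day window closes at day 170, and FU2 is at day 213. An event starting between days 1 and 170 then has 212 down to 43 days of observation.

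- a = 43, b = 212: ongoing 30/169 × (0.2385 − 0.0009) = 4.2%; hidden 15/169 × 0.0569 = 0.5% of two-cluster participants, or 12% of those with an ongoing second cluster.
- FU2 seven days early (a = 36, b = 205): hidden 15/169 × 0.0907 = 0.8%.
- Much shorter follow-up, a = 1: with b = 100, hidden/ongoing = 0.1416/0.2823 = 50%; with b = 30, 0.4139/0.6200 = 67%.

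The result is driven almost wholly by assumed follow-up.

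**The case against.** The best defence is that little information is lost. A participant left out of the IMM table remains in the main select-AE resolution analysis, and the by-subject listing in SAP 7.6.7.1 shows every episode. The Grade 3-5 table already discards low-grade clusters, so a treated Grade 3 event is not displaced there by a longer untreated Grade 1 event. The IMAE summaries in SAP 7.6.8 escape the longest-event condition altogether, and non-endocrine IMAEs are treated by definition. Reporting the longest episode, with a median that leans long, is cautious for a safety table. Protocol Table 2-3 requires treatment-related toxicities to be followed until they resolve, return to baseline or are judged irreversible, so a hidden ongoing event should be uncommon.

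All of this stands, and it limits the point to a minor one. It does not remove it. The any-grade IMM table still selects on the quantity it reports. The IMAE route uses a different event definition and a 100-day window, so it does not replace the select-AE table. A participant could appear in the IMAE table and be missing from the select-AE one. Arm C participants, those who withdraw and those who miss late nivolumab doses have less scheduled follow-up than the 43 to 212 days used above.

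**Conclusion.** The point holds in limited form. In the select-AE analysis, the IMM condition is applied after the longest cluster has been chosen. This omits participants whose treated cluster is not their longest, mainly in the any-grade table, and tends to lengthen the median. Percent resolved can miss an ongoing cluster shorter than a resolved one in the same participant and category.

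Only participants with two or more separate clusters in a category are touched. The documents do not say how many there will be, so the overall size is unknown; for percent resolved it is probably small.

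A reader might infer three stronger things that the documents do not support:

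- That ongoing events drop out generally. Appendix 1 censors an ongoing longest cluster and treats it as unresolved.
- That the median is inflated by some 77% (36.9 against 20.8 days), or that half to two-thirds of ongoing second episodes are counted as resolved. Both figures belong to an assumed two-cluster subgroup with assumed durations, and the second also assumes follow-up that may be as short as one day.
- That these tables are the plan's only account of whether immune toxicity reverses. The IMAE summaries cover the same ground.

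**What to change.** In SAP 7.6.7.3 and Appendix 1:

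1. For the IMM analysis, first restrict to clusters during which IMM was started, then take the longest of those for each participant and category.
2. Beside the existing percentage, report the percentage of participants with all clusters in the category resolved (for the IMM table, all IMM-treated clusters).

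Leave the Kaplan-Meier cluster selection otherwise unchanged. Ranking any unresolved cluster above a resolved one would bring in a new selection on outcome: a known 40-day resolved event could be replaced by a 2-day censored record.

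The cost is about two sentences, one reordered derivation step and one extra row per table. The added percentage can only equal or fall below the present one when both are taken over the same participants and clusters. The IMM tables will no longer match any already produced with the present selection order.

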### **7.6.8 Immune-Mediated Adverse Events (US Submission)**

IMAEs will be summarized by treatment group for each immune-mediated category / PT using the 100-day safety window:

- Overall summary of non-endocrine IMAEs by worst CTC grade (any grade, grade 3-4, grade 5) where immune modulating medication was initiated presented by Category / PT.
- Overall summary of endocrine IMAEs by worst CTC grade (any grade, grade 3-4, grade 5) presented by Category / PT.
- Overall summary of non-endocrine IMAEs leading to discontinuation by worst CTC grade (any grade, grade 3-4, grade 5) where immune modulating medication was initiated presented by Category / PT.
- Overall summary of endocrine IMAEs leading to discontinuation by worst CTC grade (any grade, grade 3-4, grade 5) presented by Category / PT.
- Overall summary of non-endocrine IMAEs leading to dose delay or reduction by worst CTC grade (any grade, grade 3-4, grade 5) where immune modulating medication was initiated presented by Category / PT
- Overall summary of endocrine IMAEs leading to dose delay or reduction by worst CTC grade (any grade, grade 3-4, grade 5) presented by Category / PT.
- Summaries of time-to onset and time-to resolution of non-endocrine IMAEs where immune modulating medication was initiated presented by Category.
- Summaries of time-to onset and time-to resolution of endocrine IMAEs presented by Category.

A by-subject listing of IMAEs will be provided. By-subject listings of time-to resolution for longest IMAEs cluster (any grade and grade 3-5 in separate summaries) will also be provided. For new studies which collect investigator assessment of potential IMAE data, a by-subject listing of AEs considered as immune-mediated events per investigator but not qualified for IMAEs definition will also be provided.

In addition, for all nivolumab treated subjects who experienced at least one IMAE, the following data presentation will be provided:

- Summary of subjects who were re-challenged with nivolumab by IMAE category, with extended follow-up.
- Summary of subjects who were re-challenged with nivolumab by IMAE category, with extended follow-up.

For these, re-challenge is considered to have occurred when last nivolumab infusion was administered after the onset of an IMAE.

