3 INTRODUCTION

CA2097A8 is an open-label, randomized, non-comparative Phase 2 study assessing nivolumab, plus palbociclib, and anastrozole as either concurrent or phased neoadjuvant treatment for men and postmenopausal women with primary breast cancer (BC) ≥ 2 cm that are estrogen receptor-positive (ER+) and human epidermal growth factor receptor 2-negative (HER2-) with safety run-in.

Nivolumab (BMS-936558) is a fully human, IgG4 (kappa) isotype monoclonal antibody (mAb), an immuno-oncologic (IO) checkpoint inhibitor that binds programmed cell death-1 (PD-1) on activated immune cells and disrupts engagement of the receptor with its ligands programmed death-ligand 1 (PD-L1; B7-H1/CD274) and programmed death-ligand 2 (PD-L2; B7-DC/CD273), thereby abrogating inhibitory signals and augmenting the host anti-tumor response. Palbociclib is an orally bioavailable and highly selective small-molecule inhibitor against cyclin-dependent kinases (CDK)4/cyclin-D1 and CDK6/cyclin-D3 enzyme complexes, lead to reactivation of retinoblastoma (Rb) protein, binding back of E2F transcription factor and subsequent cell cycle arrest, thus abrogating endocrine-resistant cell proliferation. Anastrozole is a reversible, third-generation, selective nonsteroidal aromatase inhibitor (NSAI) that reduces peripheral estrogen synthesis by blocking the conversion of androgens to estrogens in non-ovarian tissues. A detailed description of the chemistry, pharmacology, efficacy, and safety of the study treatments is provided in the Investigator Brochures (IBs) and package inserts.^{1,2,3,4}

The study will assess the efficacy and safety of: i) concurrent therapy with nivolumab in combination with palbociclib, and anastrozole (Arm A), ii) phased therapy with one initial priming cycle of palbociclib and anastrozole followed by nivolumab in combination with palbociclib, and anastrozole (Arm B), and iii) control treatment with palbociclib and anastrozole (Arm C). Participants with newly diagnosed, previously untreated primary ER+ and HER2- BC ≥ 2 cm will be subjected to a total 5 cycles (4 weeks per cycle) of neoadjuvant therapy before definitive surgery. Efficacy will be measured by significantly improved residual cancer burden (RCB) 0-I rate.

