8.1.1 Nivolumab Dose Discontinuation

If a participant discontinues nivolumab, the entire study treatment (CDK4/6 inhibitor and anastrozole) must be discontinued.

Nivolumab treatment should be permanently discontinued for the following:

- Any Grade 2 drug-related uveitis, eye pain, or blurred vision that does not respond to topical therapy and does not improve to Grade 1 severity within the re-treatment period OR requires systemic treatment.
- Any Grade 3 non-skin, drug-related AE lasting > 7 days or recurs, with the following exceptions for laboratory abnormalities, drug-related uveitis, pneumonitis, bronchospasm, neurologic toxicity, hypersensitivity reactions, infusion reactions, and endocrinopathies:
 - Grade 3 drug-related uveitis, pneumonitis, bronchospasm, neurologic toxicity, myocarditis, hypersensitivity reaction, or infusion reaction of any duration requires discontinuation.
 - Grade 3 drug-related endocrinopathies, adequately controlled with only physiologic hormone replacement do not require discontinuation. Adrenal insufficiency requires discontinuation regardless of control with hormone replacement.
 - Grade 3 drug-related laboratory abnormalities do not require treatment discontinuation except:
 - ◆ Grade 3 drug-related thrombocytopenia > 7 days or associated with bleeding requires discontinuation.
 - ◆ Grade ≥ 3 drug-related AST, ALT, or total bilirubin requires discontinuation (see below).
 - ◆ Concurrent AST or ALT > 3 \times ULN and total bilirubin > 2 \times ULN.

NOTE: In most cases of Grade 3 AST or ALT elevation, study treatment will be permanently discontinued. If the Investigator determines a possible favorable benefit-risk ratio that warrants continuation of study treatment, a discussion between the Investigator and the Medical Monitor/designee must occur.

- Any Grade 4 drug-related AE or laboratory abnormality (including, but not limited to, creatinine, AST, ALT, or total bilirubin), except for the following events which do not require discontinuation:
 - Grade 4 neutropenia ≤ 7 days.
 - Grade 4 lymphopenia or leukopenia or asymptomatic amylase or lipase elevation.
 - Isolated Grade 4 electrolyte imbalances/abnormalities that are not associated with clinical sequelae and are corrected with supplementation/appropriate management within 72 hours of their onset.

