## 6 STUDY PERIODS, TREATMENT REGIMENS AND POPULATIONS FOR ANALYSES

### 6.1 Study Periods

- Baseline period:
  - Baseline evaluations or pre-treatment events will be defined as evaluations or events that occur before the date and time of the first dose of study treatment. Evaluations (laboratory tests, pulse oximetry, vital signs [REDACTED]) on the same date and time of the first dose of study treatment will be considered as baseline evaluations. Events (AEs) on the same date and time of the first dose of study treatment will not be considered as pre-treatment events.
  - In cases where the time (onset time of event or evaluation time and dosing time) is missing or not collected, the following definitions will apply:
    - ◆ Pre-treatment AEs will be defined as AEs with an onset date prior to but not including the day of the first dose of study treatment;
    - ◆ Baseline evaluations (laboratory tests, pulse oximetry, vital signs [REDACTED]) will be defined as evaluations with a date (and time if collected) on or prior to the date of first dose of study treatment.
  - If there are multiple valid observations in the baseline period, then the latest non missing observation will be used as the baseline in the analyses. If multiple observations exist on the latest collection date (and time if collected), the record with the latest data entry date and time will be used. If multiple observations exist on the latest collection date (and time if collected) and data entry date and time, then the first observation is used as baseline, unless otherwise specified.

- ◆ Refer to the study-specific protocol for potential additional baseline evaluations definition such as baseline tumor evaluation, etc.
- Post baseline period:
  - On-treatment AEs will be defined as AEs with an onset date and time on or after the date and time of the first dose of study treatment (or with an onset date on or after the day of

first dose of study treatment if time is not collected or is missing). For subjects who are off study treatment, AEs will be included if event occurred within a safety window of 30 days (or 100 days depending on the analysis) after the last dose of study treatment. No “subtracting rule” will be applied when an AE occurs both pre-treatment and post-treatment with the same preferred term and grade.

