### **7.1.1.3 Immune-Mediated Adverse Events (US Submission)**

In order to further characterize AEs of special clinical interest, analysis of immune-mediated AEs (IMAE) will be conducted. IMAEs are specific events (or groups of PTs describing specific events) that include pneumonitis, diarrhea/colitis, hepatitis, nephritis/renal dysfunction, rash, endocrine (adrenal insufficiency, hypothyroidism/thyroiditis, hypothyroidism, thyroiditis, hyperthyroidism, diabetes mellitus, and hypophysitis), and other specific events, considered as potential immune-mediated events by investigator that meet the definition summarized below:

- those occurring within 100 days of the last dose,
- regardless of causality,
- treated with immune-modulating medication (of note, endocrine AEs such as adrenal insufficiency, hypothyroidism/thyroiditis, hypothyroidism, thyroiditis, hyperthyroidism,

diabetes mellitus, and hypophysitis are considered IMAEs regardless of immune-modulating medication use, since endocrine drug reactions are often managed without immune-modulating medication).

- with no clear alternate etiology based on investigator assessment, or with an immune-mediated component.

The list of MedDRA preferred terms used to identify IMAEs is revisited quarterly and updated accordingly. The preferred terms used for the selection at the time of the database lock by categories will be provided.

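### The SAP's re-challenge rule does not require nivolumab before the immune-mediated event, so a first-ever infusion in Arm B can be reported as re-challenge, and continued and resumed dosing are pooled

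*SAP*

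**What the plan says.** **The rule.** SAP Section 7.6.8 plans a summary of re-challenge by IMAE category: "for all nivolumab treated subjects who experienced at least one IMAE, the following data presentation will be provided". The operational definition is that "re-challenge is considered to have occurred when last nivolumab infusion was administered after the onset of an IMAE". Neither document defines re-challenge anywhere else.

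**What counts as an IMAE.** SAP Section 7.1.1.3 sets these conditions:
- The event is one of the listed types and the investigator considers it potentially immune-mediated.
- The window is "those occurring within 100 days of the last dose", with the drug not named.
- Events count "regardless of causality".
- Immune-modulating medication was given, a condition waived for endocrine events.
- The event is one "with no clear alternate etiology based on investigator assessment, or with an immune-mediated component".

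**When counting starts.** SAP Section 7.1.1 restricts adverse event tables to on-treatment events unless stated otherwise. SAP Section 6.1 reads: "On-treatment AEs will be defined as AEs with an onset date and time on or after the date and time of the first dose of". The sentence goes on to name the whole study regimen, so the clock is not tied to nivolumab.

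**Arm B.** Protocol Section 5.1.2.2 and Table 2-2 give palbociclib plus anastrozole alone in Cycle 1, with nivolumab from Cycle 2 Day 1 for four cycles.

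**The concern.** Nobody can be re-challenged with a drug they have not yet received. In Arms A and the safety run-in, nivolumab starts in Cycle 1, so every on-treatment IMAE that precedes a later infusion has nivolumab before it, apart from timing within the first day. In Arm B that does not hold, and the SAP rule has no condition to catch the difference. Because IMAEs are summarized by treatment group, the error falls on one arm only, in a trial that studies concurrent against phased dosing side by side.

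A second, weaker matter affects all nivolumab groups. The rule does not ask whether a dose was omitted. Someone whose event never interrupted dosing and someone who stopped and later resumed appear in the same count. Protocol Sections 7.4.4.1 and 7.4.4.2 treat omission and resumption as a sequence with its own criteria, so a reader of the table would want to tell the two groups apart.

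**Working it through.** The documents state no figure on this point, so there is none to reproduce. The check applies the SAP rule to the planned schedule.

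**Inputs**
- Cycle length 28 days, at most 5 cycles (SAP Section 2.1).
- Arm A infusions on Day 1 + 28k, k = 0 to 4: Days 1, 29, 57, 85, 113.
- Arm B infusions start at Cycle 2 Day 1: Days 29, 57, 85, 113.
- Rule: flagged if last infusion day > IMAE onset day.

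**Onset days that trigger the rule when all planned infusions are given**

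| Arm | Flagged onset days | Number | Before any nivolumab |
|---|---|---|---|
| A | 1 to 112 | 112 | 0 |
| B | 1 to 112 | 112 | 28 (Days 1-28) |

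Arm B share: 28 / 112 = 25% of flagged onset days.

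**Individual cases**
- Arm B, onset Day 15, one infusion only, on Day 29: 29 > 15, flagged. This is a first exposure.
- Either arm, onset Day 40, every planned infusion given: 113 > 40, flagged, with no dose omitted.
- Arm A, onset Day 40, last infusion Day 29: 29 < 40, not flagged.
- Arm A, onset Day 120, last infusion Day 113: not flagged.

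**Can an IMAE occur without an omission?** Protocol Section 7.4.4.1 lists omission for Grade 2 non-skin drug-related events (fatigue excepted), for Grade 3 skin drug-related events and for certain laboratory abnormalities. It also allows omission on investigator judgment. Grade 1 events, Grade 1-2 skin events and events judged not drug-related are not listed triggers. Since IMAEs count whatever the causality, such events can enter the table with dosing uninterrupted.

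**With a prior-exposure condition added**, the 28 pre-nivolumab onset days in Arm B give no flags, leaving 112 - 28 = 84. The count in Arm A is essentially unchanged. No IMAE rates are given, so none of these day counts converts to a number of participants.

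**The case against.** **Few Arm B cases may qualify.** An event in Cycle 1 must still be considered potentially immune-mediated by the investigator, in an open-label trial where the investigator knows that nivolumab has not been given. Protocol Section 9.2.9 links these events to immuno-oncology agents and names nivolumab as the one in this protocol. This stands as a limit on size. It does not remove the error, because nothing excludes such events. A reader might infer that any Cycle 1 thyroid event qualifies. It does not: only the medication condition is waived for endocrine events, not the investigator filter.

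**The definition is the sponsor's to choose.** A reader might infer that re-challenge must mean resuming after a withheld dose. Neither document says so, and the SAP states its rule openly. The rule may be a shared convention: the SAP cites an IO Core SAP that was not available for this review. This stands, and it is why the second matter calls for a split of the count, not a new definition. It does not rescue a convention that presumes nivolumab from Day 1 when applied to Arm B.

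**Controlled endocrine events.** A reader might cite Protocol Section 8.1.1, "Grade 3 drug-related endocrinopathies, adequately controlled with only physiologic hormone replacement do not require discontinuation", to argue that these participants continue without a gap. That sentence concerns discontinuation, not omission. Section 7.4.4.1 calls for omission from Grade 2 for non-skin drug-related events, and Section 7.4.4.2 speaks of controlled endocrinopathies resuming. Many of them may be genuine omit-and-resume cases.

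**The information exists elsewhere.** SAP Section 7.6.8 also tabulates IMAEs leading to dose delay or reduction, Section 7.4.2 summarizes omitted nivolumab doses with reasons, and Section 7.4.1 lists dosing by subject. A reader could separate the groups by hand. This is true, but the re-challenge table itself would remain wrong for Arm B.

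**Conclusion.** The rule as written gives a wrong result for any Arm B participant who has a qualifying IMAE on Days 1-28 and then receives nivolumab. Nothing else in either document corrects it. The pooling of continued and resumed dosing is also literally present in all nivolumab groups; it is a loss of clarity and not an error against a stated definition.

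The size is bounded only in days: a quarter of Arm B's flagged onset days, assuming the planned schedule and all infusions given. The Arm B cases are probably few, and the never-omitted group is probably the larger of the two, but neither can be counted.

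Three further inferences go beyond the documents:
- *Each case moves the result by 1/40 = 2.5 percentage points of Arm B.* The presentation covers nivolumab-treated participants with at least one IMAE, by category, so 40 is not its denominator.
- *The table will consist mostly of uninterrupted continuations.* No event rates are given.
- *It makes resumption look safer than it is.* The SAP attaches no recurrence rate, tolerance claim or decision rule to this summary.

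This is one descriptive safety table. It does not touch the efficacy endpoints or dose decisions.

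**What to change.** 1. Add to the rule in SAP Section 7.6.8: *and at least one nivolumab infusion was administered before the onset of that IMAE*.
2. Report Arm B IMAEs with onset before the first nivolumab infusion in a separate row.
3. Otherwise keep the sponsor's count, but split it into *at least one nivolumab dose omitted between onset and the last infusion* and *continued without omission*.

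Derive the split from dosing records and the adverse event action-taken field (SAP Sections 7.1.1, 7.4.1 and 7.4.2). Do not require the omission to carry that particular IMAE as its recorded reason: the documents do not show that the CRF links an omitted dose to a specific event. Count omitted doses only, since an infusion paused and restarted on the same day (SAP Section 7.4.2.1) is not an omission.

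The two re-challenge bullets in Section 7.6.8 are word-for-word identical, so one intended output cannot be identified; settle that in the same edit.

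The cost is SAP wording and one or two extra table rows, with slightly smaller re-challenge counts. If the rule is shared across studies, the split subtotals can be added back together, and with the separate Arm B row they recover the count under the present rule.
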